ANOVA will be used to compare the change in the intervention group to the change in the control group for the following primary outcomes, AIM 1: (1) functional performance, (2) aerobic capacity, (3) diastolic function; AIM 2: (1) strength, (2) muscle mass. In the ANOVA models, the change from baseline to 16-weeks will be the dependent variable in models adjusted for the baseline value of the outcome measure and treatment group. Groups will be compared at baseline for differences in potential confounders such as age and comorbidity. Additional adjustment will be made if the randomization produces groups that are not balanced on factors which are also associated with outcomes. We do not anticipate needing to adjust for sex, history of AIDS, or length of HIV infection (CD4 cell count) as our group assignment will be blocked on these factors. Similar analyses will be performed for secondary outcomes, intramuscular fat,

percent body fat, plasma glucose, insulin, and lipids, blood pressure. All analyses will be two-tailed.

We will use regression analyses to test the following associations, Specific aim 1: change (16-week value minus baseline value) in VO₂peak with change in (1) diastolic function and (2) markers of systemic chronic inflammation, (3) change in diastolic function with change in myocardial fibrosis; Specific Aim 2 (1) change in strength with change in muscle mass, (2) change in muscle mass with change in markers of inflammation, change in intramuscular fat with change in (3) plasma lipid and (4) fasting glucose concentrations. These analyses will be adjusted as noted above, except they will not be adjusted for group as the analytic interest lies in the relation of change to change, not change to group.

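### The change-on-change regressions choose covariates by arm balance and blocking, which does not protect the slope of one non-randomised change on another

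*Combined protocol and SAP*

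**What the plan says.** The SAP's Statistical Analyses section first sets the covariate rule for the ANOVA of change between arms. It describes "models adjusted for the baseline value of the outcome measure and treatment group". It then says "Groups will be compared at baseline for differences in potential confounders such as age and comorbidity", and "Additional adjustment will be made if the randomization produces groups that are not balanced on factors which are also associated with outcomes". For three further factors it says "We do not anticipate needing to adjust for sex, history of AIDS, or length of HIV infection (CD4 cell count"), and the reason given is "as our group assignment will be blocked on these factors".

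The next paragraph sets out the regressions of change on change: three under Specific Aim 1 (VO₂peak with diastolic function, VO₂peak with inflammation, diastolic function with myocardial fibrosis) and four under Specific Aim 2 (strength with muscle mass, muscle mass with inflammation, intramuscular fat with lipids, intramuscular fat with glucose). For all seven the covariates are settled in one clause, "These analyses will be adjusted as noted above", with treatment group as the only exception. The stated reason for dropping group is that "the analytic interest lies in the relation of change to change, not change to group". The documents give no other confounder set for these models, no threshold for imbalance, and none for association with outcome.

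**The concern.** The ANOVA and the regressions ask different questions. In the ANOVA the exposure is the arm, which is randomised, and a factor can distort the result only to the extent that it differs between arms. In the regressions the exposure is another change measured in the same participant, which nobody randomised. A factor that influences both changes produces a slope between them whether or not the arms are balanced on it. Blocking on sex breaks the link between sex and arm. It does nothing to the link between sex and either change.

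The plan therefore states that its interest is change to change, yet decides which covariates enter by a change-to-arm criterion. This is separate from leaving treatment group out of the models, and it remains when group is put back.

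At stake is how these slopes are read. The hypothesis in the Protocol Overview holds that the fitness gain works through diastolic function and goes along with lower inflammation. The VO₂peak regressions in Aim 1 are the only planned analyses that relate those changes to each other.

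**Working it through.** **Inputs from the documents.** 22 per group, so n = 44; two-sided alpha 0.05 (Power Analyses); the covariate rule described above. The 22 per group cannot be reproduced, because no difference or SD is printed. Back-solved, it gives 80% power at a standardised difference of (1.960 + 0.842) × √(2/22) = 0.845 by the normal formula, or 0.865 by the t distribution. The point does not rest on that figure.

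**Assumptions, not in the documents.** One baseline factor C has correlation r with each of two changes that are otherwise unrelated. C acts equally in both arms. Exercise shifts neither change (relaxed in step 4). The plan's rule is taken to add C if the arms differ on it at p<0.05 (alternatively p<0.20) and C is associated with the outcome at p<0.05.

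**Step 1: formula with C left out.** The induced correlation between the two changes is r × r. With the outcome's baseline value in the model, the shift on the Fisher scale is m = atanh(r²) × √(44 − 3 − 1), and the rejection rate is Φ(−1.96 + m) + Φ(−1.96 − m). For r = 0.4: atanh(0.16) = 0.1614, m = 0.1614 × 6.325 = 1.021, and the rate is Φ(−0.939) + Φ(−2.981) = 0.174 + 0.001 = 17.5%.

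**Step 2: simulation of the plan's rule** (5,000 to 20,000 trials per setting; ranges show the spread over repeated runs).

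| r with each change | Induced correlation | Formula, C left out | Plan's rule, p<0.05 trigger | Plan's rule, p<0.20 trigger | C always in |
|---|---|---|---|---|---|
| 0.2 | 0.04 | 5.7% | 5–6% | 5.5% | about 5% |
| 0.3 | 0.09 | 8.8% | 8–9% | 8.5% | about 5% |
| 0.4 | 0.16 | 17.5% | 16–17% | 15% | about 5% |
| 0.5 | 0.25 | 36.5% | 35–36% | 31% | about 5% |

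With the p<0.05 trigger the rule brings C in about 1–5% of the time, so it behaves almost like no adjustment. With C made exactly equal in the two arms and left out, the rates are 5.6%, 8.6%, 17% and 36%. Balance therefore gives no protection. Adding treatment group but not C gives 9%, 17% and 36% at r = 0.3, 0.4 and 0.5. If the outcome's baseline value correlates −0.4 with its change, the plan's rule still gives 9%, 19% and 41% at those values, so the always-included baseline value is no cure.

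**Step 3: factor acting only in the exercise arm**, group in the model. At r = 0.3, 0.4 and 0.5 within that arm, the false-positive rate is about 6%, 8–9% and 12–15%. Entering C as a single main effect as well leaves 6–7%, because one common slope does not fully describe a factor that acts in one arm.

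**Step 4: exercise shifts both changes.** Take a shift of 0.866 SD in each, close to the difference detectable with 22 per group. Arm alone then induces a correlation of (0.866²/4) / (1 + 0.866²/4) = 0.1875/1.1875 = 0.158.

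| r with each change | C in, group out | Group in, C out | Both in |
|---|---|---|---|
| 0 | 17–18% | 5% | 5% |
| 0.3 | 19–21% | 9% | 5% |
| 0.5 | 25–27% | 37% | 5% |

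Neither correction replaces the other.

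**The case against.** The plan calls these regressions tests of association. Only the VO₂peak and diastolic function pair matches the mediation wording of the hypothesis, and for inflammation the hypothesis claims no more than correlation. A correlation that arises from a common cause is still a correlation. That stands, and it lowers the severity. It does not rescue the rule: the sponsor has chosen to adjust these models, and the criterion for doing so does not fit them.

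The size rests on correlations that nobody has supplied. At 0.2 the inflation is negligible, and a factor that merely blunts response to training acts mainly in the exercise arm, where the effect is smaller. Both points stand. The triggers are also assumed.

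Four stronger readings are tempting, and the documents do not support them:

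- A reader might infer that sex, AIDS history and CD4 count can never be adjusted for. The plan says only that it does not expect to need to. What fails is the reason it gives, which is blocking.
- A reader might infer that a positive mechanism finding from this trial would be false. The calculation shows that it could be, under correlations of about 0.3 or more. It does not show that it is likely.
- A reader might infer that baseline covariates alone bring the error back to 5%. They do so only if exercise moves neither change, which is contrary to the trial's premise.
- A reader might apply the enrolled number, 44/(1 − 0.30) = 63, and find higher rates. No enrolment target is printed, and participants whose 16-week values are both imputed add little information on the slope, so 44 is the safer basis.

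**Conclusion.** The concern holds as a should-fix. The stated rule leaves common causes of the two changes unadjusted in all seven regressions, and balance or blocking between arms does not change that. The consequence runs from nil (r of 0.2) to serious (about 16% at 0.4 and 36% at 0.5, against a nominal 5%). It depends on correlations the documents do not give, and on the assumptions of no true link, no exercise effect, n = 44, a factor acting equally in both arms and a p<0.05 trigger. The randomised comparisons of the primary outcomes are not touched, so a reading that the trial's main results are at risk would go too far.

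**What to change.** In the regression paragraph of Statistical Analyses, replace the cross-reference to the ANOVA rule with a short prespecified covariate set for all seven models: baseline value of the outcome, age, sex, one named comorbidity measure, and CD4 count/AIDS history. State that these enter regardless of arm balance or blocking. Report each model with treatment group included as well, since step 4 shows that baseline covariates alone do not restore the error rate if exercise shifts both changes.

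The cost is wording plus degrees of freedom. The plan already compares arms on age and comorbidity and blocks on the remaining factors, so no new data are needed. With 44 participants, a model holding the intercept, exposure and baseline value has 44 − 3 = 41 residual degrees of freedom. Four or five more terms leave 37 or 36, and the version with group leaves one fewer. That is a real loss of precision in a trial this small, and a reason to keep the set short.

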TITLE: Strength Training and Endurance Exercise for LIFE

Trial # NCT02102060
Registered 3/27/2014

Principal Investigators

[name], ScM,^{1,2}
[name]^{3,4}

1 Salem Veterans Affairs Medical Center, Salem, Virginia

2 Virginia Tech Carilion School of Medicine, Roanoke, Virginia

3 Baltimore Veterans Affairs Medical Center Geriatric Research, Education, and Clinical Center at the Veterans Affairs Maryland Health Care System

4 University of Maryland School of Medicine, Baltimore, Maryland

Funding

The research described here was supported by the Department of Veterans Affairs Veterans Health Administration, Rehabilitation Research and Development Service, I01 RX000667

Ethics approval and consent to participate

The study was approved by the Institutional Review Boards at the Salem VAMC, Salem, VA and the University of Maryland IRB, Baltimore, MD.

Written informed consent was obtained from each patient prior to participation.

Protocol Overview

Hypothesis: We hypothesize that high-intensity exercise training will increase cardiorespiratory fitness, which will be mediated by improved diastolic function and will correlate with decreased biomarkers of inflammation.

Background: Adults with HIV on antiretroviral therapy have a life expectancy approaching that of the general population yet have impaired cardiorespiratory fitness and diastolic function that increase their risk for age-related disability. Chronic inflammation is a well-studied mediator of advanced aging with HIV, including cardiac dysfunction, yet the impact of exercise training is unclear. The study objective is to develop an exercise program for older adults with HIV that targets pathophysiological processes of advanced aging and will prevent and improve disability.

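### The change-on-change regressions appear to adjust for the dependent variable's baseline but not the predictor's, which can bias or dilute the slope

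*Combined protocol and SAP*

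**What the plan says.** The SAP's Statistical Analyses section first sets out the between-group models. There the change from baseline to 16 weeks "will be the dependent variable in models adjusted for the baseline value of the outcome measure and treatment group". Further covariates enter only conditionally: "Additional adjustment will be made if the randomization produces groups that are not balanced on factors which are also associated with outcomes".

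The next paragraph turns to change against change: "We will use regression analyses to test the following associations". It lists three for Specific Aim 1 (VO₂peak with diastolic function, VO₂peak with inflammatory markers, diastolic function with myocardial fibrosis). It lists four for Specific Aim 2 (strength with muscle mass, muscle mass with inflammatory markers, intramuscular fat with plasma lipids, intramuscular fat with fasting glucose). Change is the raw difference, week 16 minus baseline. The covariates are given only by cross-reference: "These analyses will be adjusted as noted above, except they will not be adjusted for group". The reason offered for dropping group is that "the analytic interest lies in the relation of change to change, not change to group".

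The section does not say which member of each pair is the dependent variable. It gives no covariate list, reliability, expected slope or power for these regressions.

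**The concern.** The cross-reference brings one baseline into each regression, that of the outcome measure. In a regression of change in Y on change in X, that is Y's baseline. X's baseline is not named, although it is part of the predictor by construction. People who start high on X tend to show a smaller change in X, so raw change in X is correlated with baseline X.

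Two things can follow. If baseline X forecasts change in Y given baseline Y, the coefficient on change in X picks up part of that relation. If it does not, the part of change in X that comes from baseline X is noise, and it flattens the slope. The reason given for omitting group does not bear on the predictor's baseline.

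The Protocol Overview hypothesises a fitness gain "which will be mediated by improved diastolic function and will correlate with decreased biomarkers of inflammation". The Aim 1 regressions are the planned analyses that link those changes, so a biased or diluted slope affects the trial's mechanism claim.

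**Working it through.** **No plan figure to reproduce.** The Power Analyses section gives 22 per group, at least 80% power and two-sided alpha 0.05, for between-group differences only. Its means and SDs are not printed. I take n = 2 × 22 = 44. For scale, 44 completers give 80% power for a correlation of about 0.41.

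**Model (all values assumed).** Variables are standardised, with X₁ = aX₀ + u and Y₁ = 0.6Y₀ + cX₀ + v. The correlation of X₀ with Y₀ is ρ = 0.3, a is the stability of X, c is the cross-lag, and Var(u) = 1 − a². Then ΔX = −(1 − a)X₀ + u and ΔY = −0.4Y₀ + cX₀ + v. The model as written is ΔY on ΔX and Y₀; the alternative adds X₀. There is no treatment effect in this model.

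**Large-sample slope as written.** Remove Y₀ from ΔX and write D = (1 − a)(1 − ρ²) + (1 + a).
- Bias with no true link: −c(1 − ρ²)/D. For c = 0.2, a = 0.5: −0.2 × 0.91/(0.5 × 0.91 + 1.5) = −0.182/1.955 = −0.093. For a = 0.7: −0.182/(0.273 + 1.7) = −0.092. The sign reverses with the sign of c.
- Share of the slope kept when c = 0: (1 + a)/D. This is 1.5/1.955 = 0.77 at a = 0.5, 1.7/1.973 = 0.86 at a = 0.7, and 1.85/1.9865 = 0.93 at a = 0.85.

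Adding X₀ removes both effects in this error-free model.

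**Simulation, n = 44, two-sided 5%, repeated independently.** Ranges cover a = 0.5 and 0.7 and the repeat runs. The true link is a correlation of 0.4 between u and v.

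| Situation | As written | With X₀ |
|---|---|---|
| No link, c = 0.1 | 6–7% | about 5% |
| No link, c = 0.2 | about 8–12% | 4–6% |
| No link, c = 0.3 | 14–24% | about 5% |
| No link, c = −0.2 | 8–11% | about 5% |
| True link, c = 0 | 65–72% | 75–78% |
| True link, c = 0.2 | 28–47% | 75–77% |
| True link, c = −0.2 | 84–88% | 75–78% |

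The higher rejection in the last row is bias, not a gain in power: the null rate for that cross-lag is inflated too.

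**Higher stability.** At a = 0.85–0.9 and c = 0, power is about 74–75% as written against 76%. The null rate at c = 0.2 is about 6–7%. Power at c = 0.2 is still 52–58% against 75–77%.

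**Measurement error in the change score.** Let reliability be R, e = 1 − R, and true-change SD s = 0.5, with true change unrelated to baseline. The slope keeps s²/(s² + 2e) of its value as written and s²/(s² + 2e − e²) with X₀.
- R = 0.9: 0.25/0.45 = 0.556 against 0.25/0.44 = 0.568.
- R = 0.5: 0.25/1.25 = 0.20 against 0.25/1.00 = 0.25.

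So X₀ recovers little of the attenuation that comes from measurement error alone. In the first model with error added (R = 0.9, c = 0), power rises from 44% to 59% at a = 0.5 and from 44% to 54% at a = 0.7.

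**The case against.** **The omission is inferred.** The pairs are written symmetrically and most members are themselves trial outcomes, so "models adjusted for the baseline value of the outcome measure and treatment group" could be stretched to cover both baselines. The conditional adjustment could also admit the predictor's baseline, but only if the arms happened to be imbalanced on it. This stands as a limit on certainty. It is also a reason to write the models out, because two analysts could fit different ones.

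**A reader might infer that all seven tests are materially distorted and lose power.** The documents do not support that. They give no stability, reliability or cross-lag for any pair. With zero cross-lag there is no excess of false positives, with high stability the power loss at zero cross-lag is about 2 points, and with a negative cross-lag the model as written rejects more often.

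**A reader might infer that adding the predictor's baseline restores a 5% error rate whether or not group is in the model.** It does not. The regressions pool both arms. Suppose the intervention moves both variables by 0.8 baseline SD (assumed) with no within-group link. At a = 0.7 and c = 0.2, rejection is about 14% as written and 30–32% with the predictor's baseline. At an effect of 0.5 SD and a = 0.5, it is 4.8% and 9.0%. Only a group term brought it back to about 5%. One may reply that the plan targets the pooled association, but then the within-group null is not the right benchmark either. In either case this is a separate question.

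**The remedy has a cost.** With noisy baselines correlated 0.5 and no true link, adding X₀ gives a slope of +0.05 at R = 0.7 and +0.07 at R = 0.5. Type I error is then 5.9% and 7.6%, against 4.8% and 5.5% without X₀. At R = 0.9 the effect is negligible (4.9% against 5.0%).

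**Conclusion.** The point holds in a limited form. On the natural reading of the cross-reference, the predictor's baseline is left out of the seven listed associations, and no reason is given. That can bias the slope up or down, or dilute it, and neither direction nor size can be known in advance from the documents.

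Every figure above rests on assumed stability, cross-lag, baseline correlation and reliability, at n = 44. The effect is material when the predictor is only moderately stable over 16 weeks or its baseline forecasts change in the dependent variable. It is small when the predictor is highly stable and well measured and there is no cross-lag. No power is claimed for these regressions, so no stated figure is contradicted. The point does not show that the 22 per group is wrong, and it does not bear on the between-group comparisons. It is worth correcting because the mechanism hypothesis relies on these models.

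**What to change.** For each listed association, name the dependent variable and the predictor, and replace the cross-reference with an explicit sentence: *Each regression of change on change will be adjusted for the baseline value of both the dependent variable and the predictor.* Where a pair involves several markers, list each model.

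The cost is one SAP sentence, a short list of models and one degree of freedom per model. The baseline values are already collected, since each change is computed from them. With noisy, strongly correlated baselines a small residual bias remains, so reporting the slope with and without the predictor's baseline would be a sensible check. The amendment should not be described as securing a 5% error rate when the intervention changes both variables. Whether group belongs in these models has to be settled separately.

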Design: The study is a randomized trial comparing 16-weeks of progressive aerobic and resistance training to usual care in sedentary older (50+ years) adults with HIV. The center-based exercise training is performed three times weekly under supervision. The end-target duration and intensity of aerobic exercise is 45 minutes at 70-80% of baseline heart rate reserve. Resistance training progresses from low-intensity to high-intensity based on initial one repetition maximum (1-RM) in the three upper body (chest press, seated row, pull-down) and three lower body exercises (leg press, knee extension, knee flexion). Primary outcomes are cardiorespiratory fitness, cardiac function, and biomarkers of myocardial fibrosis and cardiac stress. Secondary outcomes include muscle strength, body composition measured by Dual-energy X-ray absorptiometry (DXA), and biomarkers of systemic Inflammation.

Statistical Analysis Plan (SAP)

Power Analyses

Power calculations were based on results from randomized exercise trials that included a sedentary control group. For outcomes of diastolic function¹, cytokines², and biomarkers of myocardial fibrosis³ we used mean (SD) from exercise trials in older adults without HIV since results were not available for adults with HIV. Referenced values for VO₂peak⁴ and strength⁵ were obtained from trials in adults with HIV, but a younger population (mean age 30-45 years old). For these outcomes, a sample size of 22 participants per group provides at least 80% power to detect a between group difference with a two-sided alpha of 0.05. We acknowledge that older participants may have greater muscle soreness or fatigue as well as more medical problems. Therefore, our target enrollment number assumes a conservative attrition rate of 30% based on prior exercise interventions in adults with HIV.^{6,7}

Statistical Analyses

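### The change-to-change regressions exclude treatment group by rule, so where exercise moves both variables the pooled slope can suggest a mechanism that is not there

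*Combined protocol and SAP*

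**What the plan says.** The Statistical Analyses section of the SAP lists seven regressions of change on change. Aim 1 has three: VO₂peak on diastolic function, VO₂peak on inflammation, and diastolic function with myocardial fibrosis. Aim 2 has four: strength with muscle mass, muscle mass with inflammation, and intramuscular fat with lipids and with glucose. The first is given as "change (16-week value minus baseline value) in VO₂peak with change in (1) diastolic function".

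On covariates, the section says "These analyses will be adjusted as noted above". That refers back to the between-group analyses, which are fitted "in models adjusted for the baseline value of the outcome measure and treatment group", with further adjustment for imbalanced prognostic factors. Group is then removed: "they will not be adjusted for group as the analytic interest lies in the relation of change to change, not change to group".

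The Hypothesis in the Protocol Overview gives the purpose. Exercise is to raise cardiorespiratory fitness, "which will be mediated by improved diastolic function and will correlate with decreased biomarkers of inflammation". Neither the protocol nor the SAP describes a mediation analysis, a group-adjusted version of these regressions, or a within-arm version.

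**The concern.** The SAP wants the relation between two changes apart from the effect of group. Omitting group does not give that. In a randomised trial of exercise against usual care, group can cause both changes. If it does, the exercise arm sits higher on both variables (or higher on one and lower on the other), and a line through the pooled data picks up the gap between the two arm means. The slope can then differ from zero even if, within each arm, participants with larger gains in one variable have no larger gains in the other.

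Baseline adjustment does not help, because randomised group is independent of baseline.

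What is at stake is the mechanistic claim. Only the regression of VO₂peak change on diastolic change bears on the mediation hypothesis. A significant pooled slope there could be reported as support for mediation when exercise improves the two by unrelated routes. The distortion also grows with the treatment effects and the sample size, so it is largest when the trial succeeds and a mechanism claim is most tempting.

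**Working it through.** **Inputs.** From Power Analyses: "a sample size of 22 participants per group provides at least 80% power to detect a between group difference", two-sided alpha 0.05, 30% attrition. The means and SDs behind the 22 are not given, so the figure cannot be reproduced forwards. It can be inverted.

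**Implied effect.** For a two-sample comparison, the normal approximation gives d = (1.960 + 0.842) × √(2/22) = 0.845. The noncentral t gives d = 0.865, used below. The plan says at least 80% power, so under this test 0.865 is a floor for the planned effects.

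**Where the anchor applies.** Power Analyses names diastolic function, cytokines, fibrosis markers, VO₂peak and strength. Taking cytokines as the inflammation markers, that covers both sides of the three Aim 1 regressions. It does not name muscle mass, intramuscular fat, lipids or glucose, so it covers both sides of no Aim 2 regression.

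**Sample sizes.** 22 per arm, and 22/0.7 = 31.4, so 32 per arm before attrition. The second is an upper bound, because multiply imputed participants do not add full information.

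**Pooled correlation.** With equal arms, within-arm correlation ρ, and group effects d₁ and d₂ in within-arm SD units:

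r = (ρ + d₁d₂/4) / √[(1 + d₁²/4)(1 + d₂²/4)]

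- ρ = 0, d₁ = d₂ = 0.865: d²/4 = 0.187, so r = 0.187/1.187 = 0.16.
- ρ = 0, d₁ = d₂ = 0.5: r = 0.0625/1.0625 = 0.059.
- ρ = 0, one effect zero: r = 0.
- ρ = 0.2, d₁ = d₂ = 0.865: r = 0.387/1.187 = 0.33.

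The induced part takes the sign of d₁d₂. If exercise raises fitness and lowers inflammation, it is negative, which is the hypothesised direction.

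**Rejection rates, simple regression, ρ = 0** (40,000 simulated trials, two-sided 0.05):

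| d₁, d₂ | No group, 22/arm | No group, 32/arm |
|---|---|---|
| 0.865, 0 | 5.1% | 4.9% |
| 0.5, 0.5 | 6.9% | 7.5% |
| 0.865, 0.3 | 6.8% | 7.6% |
| 0.865, 0.5 | 9.6% | 11.9% |
| 0.865, 0.865 | 17.9% | 24.5% |
| 1.0, 1.0 | 26.2% | 36.5% |

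With group in the model the rate is about 5% in every row. A separate simulation of the 0.865, 0.865 row gave 17.5% and 24.2%.

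**Rejection rates with the outcome's baseline added, as the SAP describes** (10,000 trials; d in SDs of raw change; baseline to follow-up correlation assumed to be 0.5, 0.7 or 0.8):

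- d = 0.865 on both: 20.6%, 18.8%, 18.2% at 22 per arm; 30.0%, 27.5%, 26.4% at 32.
- d = 0.5 on both: 6.6–7.0% and 7.9–8.6%.
- d = 0.865 and 0: 4.8–4.9% and 5.1–5.2%.

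Adding the predictor's baseline as well, still without group, gives 24.8%, 20.8%, 19.2% at 22 per arm for d = 0.865 on both. With both baselines and group the rate is 5.1%.

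**A real within-arm relation.** With ρ = 0.2 and d = 0.865 on both, rejection is 59.9% (22 per arm) and 76.9% (32) without group, and 25.2% and 35.4% with group.

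**The case against.** The strongest reply is that the pooled slope answers a legitimate question. The SAP speaks of testing associations, not causes, and the marginal correlation really is non-zero when exercise moves both variables. Against that null, the rejections above are correct. This stands as far as it goes: the pooled slope is a valid description. But the SAP justifies leaving group out by an interest in the relation apart from group, which the pooled slope does not isolate, and the Hypothesis goes beyond association for diastolic function.

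Second, reach. Mediation is claimed only for diastolic function. For inflammation the Hypothesis says only that the changes will correlate, which a pooled regression addresses. So the harm is greatest for one regression of seven. For the other six, reporting both models would also be defensible. The SAP's reasoning, however, is applied to all seven and is wrong for each of them.

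Third, size. The 18–30% figures need zero within-arm relation and 0.865 SD on both sides, neither of which the documents establish. With smaller or one-sided effects the rate is close to nominal. This limits the magnitude, not the principle.

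Fourth, the adjusted test is weak: 25% rejection at 22 per arm for a within-arm correlation of 0.2, so a null result must not be read as evidence against the mechanism. Most of the fall from 60% to 25% is removal of the induced association, not lost precision. Under full mediation with that within-arm correlation, the pooled test rejects only 29% of the time.

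The SAP's conditional plan to bring total training time into the analysis does not resolve the point. It is unspecified, and training time could at most stand in partly for group.

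**Conclusion.** The concern holds; the rule should be changed. The reason given for excluding group fails, and the plan contains no other analysis that could separate mediation by diastolic function from a shared effect of exercise.

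The size is conditional. The distortion arises only where exercise affects both variables. It is roughly four to six times nominal (18–30%) in the SAP's own model at 0.865 SD on both, slight (7–9%) at 0.5 SD on both or at 0.865 and 0.3, and absent if only one variable responds. All effect sizes and baseline correlations are assumptions. Confidence is high on the principle and lower on the magnitude, and the anchor applies only to the Aim 1 regressions. The randomised between-group comparisons, the power statement and the sample size are untouched.

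**What to change.** Replace the sentence that excludes group. Suggested content: each main change-to-change model includes treatment group and the baseline values of both variables, for example change in VO₂peak = group + change in diastolic function + both baselines. A pooled model without group may be reported alongside, labelled descriptive only.

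For the mediation hypothesis, do one of two things:

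- Prespecify a group-adjusted indirect effect with a bootstrap confidence interval, say how the bootstrap is combined with the planned multiple imputation, and state that it assumes no unmeasured confounding of mediator and outcome (for example by adherence or health status).
- Restate the hypothesis as an association.

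Report slopes with confidence intervals, given the low power of the adjusted tests. Group adjustment removes confounding by group only. It does not make the slope causal, because a within-arm correlation can come from another shared cause.

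The cost is one SAP sentence for the regressions, one or two degrees of freedom per model (group, and the predictor's baseline if not already included), and associations that may be weaker than the pooled ones. The mediation choice adds either one prespecified analysis or a reworded hypothesis. No new data are needed.
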